6.5 Scientific Rationale for the Study

The technology utilized by RD-X19 has been repeatedly demonstrated to provide dose dependent antiviral activity in multiple, consistent, expert-laboratory in vitro studies. The proof-of-concept clinical study EB-P12-01, established an effective dose (16 J/cm², BID) in subjects with mild-to-moderate COVID-19. The mechanism of action, including the potential to augment innate

immunity, presents an unprecedented opportunity for treatment that is not specifically antigen-directed or dependent with documented activity against SARS-CoV-2 variants which have shown increased speed of replication in human tissue. This dose range finding study is designed to select a single, safe and well-tolerated dose with the greatest likelihood of treatment benefit in a population with high prevalence of circulating SARS-CoV-2 variants.

6.5.1 Justification for Doses

In repeated laboratory experiments, including experiments conducted by external third parties with bench top LED arrays capable of delivering precise wavelengths and energy densities of light, it has been determined that the visible light emitted by the EmitBio RD-X19 device can provide potent antiviral activity against upper respiratory pathogens including SARS-CoV-2. Reduction in cell-free virus of ≥ 1000 fold and inhibition of viral replication of $\geq 99\%$ have been observed in repeated experiments conducted by the sponsor and external expert laboratories. Dose dependent effects are observed ranging from as little as a single 7.5 J/cm^2 exposure up to complete antiviral activity at 30 J/cm^2 measured 24 hours and 48 hours after exposure. Multiple cell types including human respiratory epithelial cells and 3D epithelial tissue (oral and tracheal/bronchial tissues) in culture show high viability at single doses of visible blue light up to 120 Joules/cm^2 and after several days of repeat, twice daily dosing with 32 J/cm^2 . These repeated experiments, conducted in multiple labs with multiple cell types, along with years of medical use of licensed devices with comparable wavelengths and energy, support the doses proposed in this protocol for dose finding to achieve optimal efficacy and safety for the doses tested.

As in the Phase I and Phase I/II studies of RD-X19, a primary dose and schedule of two treatments per day (separated by not less than 6 hours) will be evaluated. On Day 1, the subject will be instructed to complete two treatments regardless of time of enrollment.

In light of extant data, the current study beginning with a total energy per dose 50% increased over the previous study (EB-P12-01) will evaluate subjects over a 1 week treatment period with a follow up visit at day 14. Based on the observed safety and tolerability of Cohort A, ascending to Cohort B has been designed to deliver up to 100% increase in daily dose over the previous study and evaluate subjects over a 1 week treatment period with a follow up visit at day 14, consistent with the recommendation made by the external SMC in EB-P12-01. Cohort C, if dictated based on the safety tolerability of Cohort A, would evaluate the same daily dose delivered in EB-P12-01. The dosing schedule, duration of treatment, and ascending/descending dose design has been selected to provide clinically meaningful reductions in viral load and symptomatic relief as rapidly as possible while still maintaining a well tolerated safety profile.

Strict safety oversight will provide rapid detection of significant device-related adverse events warranting pausing or halting the trial. See Section 8.5 for detailed description of study Pausing and Stopping Rules.

7 STUDY POPULATION

The study population is outpatients ages 18 to 65 confirmed to be infected with SARS-CoV-2 who have signs and symptoms consistent with mild to moderate COVID-19. Subjects presenting with severe disease at the time of screening are excluded. Study subjects must self-report symptom onset within 72 hours or less and separately have a positive COVID-19 antigen test at screening (or within the past 24 hours of screening).

Categorization of COVID-19 disease severity will be defined as follows:

Mild COVID-19

- Positive testing by an FDA authorized SARS-CoV-2 diagnostic test, and
- Symptoms of mild illness with COVID-19 that could include fever, cough, sore throat, headache, muscle or joint pain, unexplained chills or sweats, nausea (with or without vomiting) or other non-respiratory symptoms that may alter daily living (e.g. loss of taste or smell), and
- Do not have shortness of breath, dyspnea, abnormal chest imaging, or any other clinical signs indicative of Moderate or Severe COVID-19

Moderate COVID-19

- Positive testing by an FDA authorized SARS-CoV-2 diagnostic test, and
- Symptoms of moderate illness with COVID-19, which could include any symptom of mild illness or dyspnea (shortness of breath) with exertion, and
- Clinical signs suggestive of lower airway involvement, such as resting respiratory rate ≥ 20 breaths per minute or imaging indicating lower airway disease , with an oxygen saturation (SpO_2) $\geq 94\%$ on room air at sea level.

Severe COVID-19

- Positive testing by an FDA authorized SARS-CoV-2 diagnostic test, and
- Symptoms suggestive of severe systemic illness with COVID-19, which could include any symptom of moderate illness or shortness of breath at rest, and
- Clinical signs indicative of severe systemic illness, such as resting respiratory rate ≥ 30 per minute, heart rate ≥ 125 per minute, lung infiltrates $> 50\%$, or $\text{SpO}_2 < 94\%$ on room air at sea level or $\text{PaO}_2/\text{FiO}_2 < 300$ mm Hg.

The targeted number of subjects randomized per Cohort in the dose finding portion of the study is 30 individuals seronegative for SARS-CoV-2 Spike IgG antibodies (minimum 60 subjects total, with sponsors option to increase enrollment by an additional 150 total subjects to include all serostatuses after a dose has been selected based on safety for the final cohort). Based on findings in the EB-P12-01 and the hazard ratio observed for sustained symptom resolution in the proof of

concept trial, the increased sample size with an anticipated roughly equal number of antibody positive to negative individuals in the final cohort has at least 90% power in the modified full analysis set (mFAS) population to detect clinically meaningful changes in SARS-CoV-2 symptom resolution (Hazard ratio of 0.4 between active RD-X19 and Sham observed in EB-P12-01).

The target population in the full analysis set (FAS) for the Final Cohort is intended to reflect the communities largely impacted by COVID-19, possessing both seropositive and seronegative individuals from a mixture of vaccinated and unvaccinated subjects, and with a high prevalence of circulating variants. Nasopharyngeal and saliva biospecimens collected at baseline may be analyzed to obtain genetic sequencing and characterize the incidence of SARS-CoV-2 variants in the study population.

Subject Inclusion and Exclusion Criteria must be confirmed by a study clinician, licensed to make medical diagnoses.

7.1 Study Volunteer Selection, Retention & Compensation

7.1.1 Recruitment

Potential subjects may learn about the study via IRB-approved recruitment strategies, including direct mailing, recruitment from an IRB-approved trial registry, radio announcements, digital advertisements and local advertisements/flyers. Pre-screening may begin with a brief IRB-approved telephone call from study staff. Information about the study will be presented to potential subjects and questions about their health and ability to comply with the study visit schedule will be asked of potential subjects to presumptively determine eligibility. Appointments will be made at the clinical trial unit for potential subjects who are interested in the study for further screening procedures and additional protocol-specific information.

7.1.2 Retention

Study retention strategies will include education and explanation of the study schedule and procedures during screening and enrollment visits and restriction of enrollment to persons who can attend all study visits. Participating subjects will be reminded of subsequent visits during each visit, with emphasis on completing the entire visit schedule even after disease resolution. Between visits on Days 2 and 4, to assist with retention and reinforce adherence to at-home study procedures, study personnel will contact each subject via phone. Study staff may also contact subjects prior to appointments to ensure adherence to the trial protocol. Study staff will contact subjects who miss appointments to encourage them to return for completion of safety evaluations.

7.1.3 Compensation Plan for Subjects

Subjects will be compensated for their participation in this trial. Compensation will be ultimately subject to local IRB approval. Reimbursements will be disbursed at specific timepoints during the

study with the total amount contingent on presenting up to date diary card entries and completing study procedures through day 14.

7.1.4 Costs

There is no cost to subjects for the research tests, procedures/evaluations or study device while taking part in this trial. Procedures and treatment for clinical care may be billed to the subject's insurance or third party.

8 STUDY DEVICE

8.1 Regulatory Considerations

8.1.1 Preliminary Regulatory Pathway for EmitBio™ RD-X19

The Food and Drug Administration (FDA) plays a critical role in protecting the United States from threats such as emerging infectious diseases, including the COVID-19 pandemic. To date, the agency has utilized various mechanisms to expand access for drugs, grant emergency use authorization (EUA) for certain diagnostic and treatment approaches and has issued policies for medical devices without premarket notification during the COVID-19 public health emergency.

Risk management activities have been completed according to EmitBio's SOP for Risk Management and a Risk Management Plan was developed, which are compliant with the applicable 21 CFR part 820 regulations, ANSI AAMI ISO 14971, and ISO TR 24971. A Hazard Analysis, including a Failure Effects Mode Analysis, of the device characteristics and use was performed based on ANSI AAMI ISO 14971.

The risks identified, mitigation measures and control strategies, in combination with a review of all available nonclinical and clinical safety information, has led the company to conclude that the RD-X19 operating at the proposed fluence levels is a Nonsignificant Risk Device.

Per the FDA guidance document titled "Significant Risk and Nonsignificant Risk Medical Device Studies," NSR device studies do not have to have an Investigational Device Exemption (IDE) application approved by FDA prior to initiation.

8.1.2 Proposed Label Claim/Indication for Use:

The EmitBio™ RD-X19 device is intended for use as a treatment for mild to moderate COVID-19 in subjects with positive results of direct SARS-CoV-2 viral testing ages 18 years of age and older who are symptomatic for no more than 3 days.

RD-X19 is not intended for individuals who have respiratory distress with clinical signs indicative of severe systemic illness such as a respiratory rate ≥ 30 breaths per minute, heart rate ≥ 125 per minute, SpO₂ $< 94\%$ on room air, or a ratio of arterial partial pressure of oxygen to fraction of inspired oxygen (PaO₂/FiO₂) < 300 mm Hg.

8.1.3 Medical Device Quality System:

EmitBio™ will operate under an established Quality Management System, with a commitment for continuous improvement and effectiveness, in accordance with the requirements of the customers and applicable international standards. Specifically, the EmitBio™ Quality Management System is compliant with the requirements of the FDA Quality Systems Regulations (QSR).

8.2 Study Device and Use

8.2.1 Device Description

The RD-X19 device is designed to emit safe, visible light to eliminate SARS-CoV-2 and stimulate host defenses in the oropharynx and surrounding tissues. The RD-X19 device does this without additional photosensitizers or chemical reagents that are typically employed with traditional photodynamic therapeutics.

The device consists of three components: (1) Aluminum housing, (2) Light Engine, and (3) Light Guide Assembly; each designed to allow the assembled device to meet specific criteria based on targeted safety and efficacy.

There are two primary accessories required for use of the device. The first accessory, the AC adapter, is used for recharging the device. The AC adapter is plugged into wall voltage and then connected to the device via a micro USB cable between device uses. The user is prompted, via indicator lights, when recharging is necessary, in progress, and complete. The second accessory, the stand, is used for storing the device between uses.

8.3 Use / Storage & Maintenance / Accountability

8.3.1 Acquisition and Accountability

The sponsor will provide clinical sites with RD-X19 devices packaged in appropriately labelled containers containing all components as well as instructions for use by study participants. Each RD-X19 device will be stamped on its power unit with a serial number. Study staff will ensure that each device's serial number (e.g. EB-123) is assigned to a specific study subject and the link between device serial number and study subject study number will be maintained on an accountability log. Subjects will be requested to bring their device to the clinic for each scheduled visit. Upon completion of a subject's treatment regimen in the trial, all RD-X19 devices and components must be returned to the study site and then to the study sponsor.

8.3.2 Device Storage and Maintenance

All RD-X19 devices will be stored in a locked device storage room at the clinical trial site until needed for assignment to an enrolled study volunteer. Upon acquisition by the study subject,

devices should be stored in a dry climate-controlled environment in the original container in which it was provided.

The device should be stored securely out of the reach of children who may mistakenly misuse the device, especially illumination of eyes – which is always to be avoided. The mouthpiece of the device is removable for rinsing with mild soap and warm water. The power housing may be cleaned with a soft cloth that has been dampened in mild dish detergent diluted in water; pieces should then be dried with a soft cloth. The optic of the device can be wiped gently with a dry cloth suitable for cleaning optical glasses.

8.3.3 Preparation for Use and Use

[Refer to Appendix 1: RD-X19 Investigational Device Manual]

8.4 Measures to Maximize Study Subject Compliance

Subjects will be randomized in a 2:1 ratio (RD-X19:Sham) in each dosing Cohort, providing a higher probability that the subjects being enrolled in the trial will receive potential treatment benefit. Subjects will receive appropriate compensation for the disruption to normal daily activities created by this protocol that also considers the frequency with which they are requesting to travel to the site, phone calls on study days 2 and 4, the twice daily journaling and treatment regimen, and the high number of biospecimens scheduled to be collected for microbiology assessments.

Additionally, the subjects will be educated on the role of their individual contribution in clinical research as it relates to developing a solution for mild to moderate COVID-19.

8.5 Device Discontinuation

8.5.1 Study Pausing Criteria

If observations of an SAE or patterns of discrete or non-resolving device-related TEAEs grade 2 or higher in the same SOC PT are observed in a single subject, dosing will be discontinued for that subject and observed at regulatory scheduled follow up visits.

EB-P20-01 enrollment in any Cohort will be paused if any of the following events occur:

- Any subject experiences a device related SAE.
- Any subject experiences laryngospasm, bronchospasm or anaphylaxis within 2 hours after treatment.
- Two (2) or more subjects experience an allergic reaction such as generalized urticaria (defined as occurring at three or more body parts) within 72 hours after treatment.
 - Potential photoallergy or phototoxicity to one or more photosensitizing drugs in the subject's medical history should be investigated in all cases.

See “Medications that Increase Sensitivity to Light: A 1990 Listing (Levine 1990).”

- Three (3) or more subjects experience a Grade 2 or higher TEAE (including local, systemic and/or clinical laboratory abnormalities), in the same SOC grouping of Preferred Terms based on the Medical Dictionary for Regulatory Activities (MedDRA) coding, considered to be related to RD-X19.

While the study is paused, attribution will be determined and assigned and the SMC will be notified that a consultation is required. Given the frequency of visits and the duration of the protocol, study device use may continue in unaffected subjects within a cohort until a recommendation is provided to unpause or terminate cohort enrollment by the SMC.

The SMC, when convened by the sponsor, will not only make a recommendation to unpause enrollment or discontinue dosing in a given cohort, but will also make a recommendation to the sponsor for ascending, or descending from Cohort A in the event safety/tolerability signals are observed with the first 24 J/cm² RD-X19 device.

A study volunteer may elect to discontinue participation in the trial at any time. Investigative staff will ask the volunteer to return for an early termination evaluation, but they are under no obligation to do so. All study subjects must return the RD-X19 device at study termination and study staff must verify that the device serial number matches the study subject to whom it was assigned.

8.5.2 Study Stopping Criteria

When a device-related SAE or two or more device-related severe TEAEs (grade 3) in the same SOC PT are observed within a given cohort, further enrollment and treatment in that Cohort will be discontinued.

8.5.3 Investigator Decision to Discontinue Subject Use of Device

A subject may be removed from the study for the following reasons post initial device use; however, whenever possible the subject should be followed for safety evaluations per protocol:

- Study non-compliance to protocol requirements that in the opinion of the participating clinical site PI or appropriate sub-investigator poses an increased risk (e.g., missing safety labs) or compromises the validity of the data.
- Lost to follow-up. A subject will be considered lost to follow-up if he or she fails to appear for a follow-up assessment. Extensive effort (i.e., generally three documented contact attempts via telephone calls, e-mail, etc., made on separate occasions) will be made to locate or recall the subject, followed by a couriered delivery of study documents to the subject's home address to determine the subject's health status. These efforts will be documented in the subject's study file.

- Medical disease or condition, or new clinical finding(s) for which continued participation, in the opinion of the participating clinical site PI or appropriate sub-investigator, might compromise the safety of the subject, interfere with the subject's successful completion of this study, or interfere with the evaluation of safety.
- If any TEAE, clinical laboratory abnormality or situation occurs such that continued participation in the study would not be in the best interest of the subject.
- The occurrence of a SAE.
- If the subject is using the device in any manner inconsistent with instructions and protocol directives and procedures.

If the subject agrees, every attempt will be made to follow all AEs through resolution or stabilization.

Subjects who withdraw or are lost to follow-up after signing the informed consent form (ICF) and use of the RD-X19 device will not be replaced. Subjects who withdraw or are withdrawn from this study after signing the ICF during screening but before use of the device may be replaced.

The reason for subject discontinuation or withdrawal from the study will be recorded on the appropriate e-CRF.

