6.3 Overall Design

Volunteers will provide written informed consent prior to initiating any screening procedures. Those meeting all screening criteria will be eligible for enrollment into the study. Study subjects

will be randomized in a 2:1 ratio within each Cohort, targeting to complete two cohorts in ascending or descending fashion based on safety/tolerability of Cohort A as follows:

Cohort A: RD-X19 24 J/cm² vs. Sham

(5 minute treatment, 2X/Day for a duration of 7 days)

Cohort B: RD-X19 32 J/cm² vs. Sham

(5 minute treatment, 2X/Day for a duration of 7 days)

Cohort C: RD-X19 16 J/cm² vs. Sham

(5 minute treatment, 2X/Day for a duration of 7 days)

Volunteers meeting all inclusion criteria and none of the exclusion criteria will be randomized in a 2:1 ratio within each cohort (30 per cohort). Assessments of study subjects will occur on study days 1, 3, 5, 8, with the final assessment visit on Day 14. Individuals who are hospitalized will be tracked until discharge or death and the date and time of these events will be captured in the study data.

This is a randomized, adaptive dose-finding study. The primary goal of the study is to evaluate multiple doses of the RD-X19 treatment device and establish evidence for safety and efficacy for a single selected RD-X19 doses compared to sham in SARS-CoV-2 infected individuals with outpatient COVID-19.

The primary efficacy outcomes are: (i) time to sustained symptom resolution in all patients (mild or moderate disease at baseline); and (ii) time to sustained symptom resolution in patients with mild disease at baseline. Other clinical and microbiological outcomes will also be assessed.

Since CMP and CBC results may not be available until study day 3, all volunteers who have significant clinical abnormalities will be immediately contacted and advised of the abnormality, discontinued from active participation in the protocol and advised regarding appropriate medical follow-up outside the study. All such study subjects will be replaced with a new volunteer.

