8.5.4 Follow-up of Study Subjects Who Discontinue Device Use

Discontinuation of study device use does not constitute discontinuation from the study, and the study procedures should be completed as indicated by the Study Schedule of Activities. If a clinically significant finding is identified, including, but not limited to, changes from baseline, after enrollment, the participating clinical trial site PI or qualified designee will determine if any change in subject management is needed. Any new clinically relevant finding will be reported as an AE.

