9.1.2 Procedures for Clinically Significant Laboratory Values or Findings

If in the judgement of the PI the finding poses a previously unknown risk to the subject or leads to a diagnosis of a disease or condition that would have disqualified the subject for enrollment, the subject will be withdrawn from the study immediately.

All clinically significant findings that occur post randomization and after the first use of the RD-X19 device will be considered TEAEs. Clinically significant lab findings based on Visit 1 lab draws are considered Medical History and not Adverse Events.

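### Protocol 8.5.3, 6.3 and 9.1.2 end study participation, not only device use, for some treated subjects; SAP 5.2.1 then censors them as non-events, so primary-endpoint data are lost that could be kept (low priority)

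*Protocol*

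**What the plan says.** **Protocol 8.5.3** is titled as an investigator decision to stop device use. Its opening reads "A subject may be removed from the study for the following reasons post initial device use", adding that "whenever possible the subject should be followed for safety evaluations per protocol". The reasons are non-compliance, loss to follow-up, a medical condition or new finding, an adverse event, laboratory abnormality or situation where "continued participation in the study would not be in the best interest of the subject", an SAE, and misuse of the device.

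**Protocol 8.5.4** states the opposite principle for subjects who only stop the device: "Discontinuation of study device use does not constitute discontinuation from the study, and the study procedures should be completed as indicated". It does not mention subjects removed from the study.

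**Protocol 6.3** deals with baseline chemistry and blood counts: "Since CMP and CBC results may not be available until study day 3", subjects with significant abnormalities are "discontinued from active participation in the protocol and advised regarding appropriate medical follow-up outside the study". All of them are to be replaced. Treatment starts on Day 1, so they may already have been dosed.

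**Protocol 9.1.2** overlaps with this. For a previously unknown risk or a disqualifying diagnosis, "the subject will be withdrawn from the study immediately". It also says "Clinically significant lab findings based on Visit 1 lab draws are considered Medical History and not Adverse Events".

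**SAP 4** keeps every randomized subject with at least one treatment in the FAS. SAP Table 14.1.1 lists significant laboratory findings and investigator discretion as reasons for study discontinuation. Table 14.1.2 shows the baseline laboratory cases as an exclusion from the per-protocol set but not from the FAS.

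**SAP 5.2.1** uses the diary of a discontinued subject only up to the discontinuation date and censors at the last assessment. It notes that no such subject can be a success, because success must hold until the Day 14 visit. COVID-19 hospitalisations are censored at 384 hours instead.

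**The concern.** Take a subject whose eight symptoms are all at grade 0 or 1 from hour 60 and who is removed on Day 5 for misusing the device. The subject could probably have gone on filling in the diary, and the entries to Day 14 would have settled the outcome. Under the plan the subject enters the primary analysis as a censored observation with no event, and stays in the risk set as unresolved until removal.

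Two things could be at stake. One is information: each such removal gives up an event that might have been observed. The other is the comparison: if sites remove more subjects from one arm, more resolutions are set aside in that arm.

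**Working it through.** **1. The plan's own power.** SAP 3.3 gives 100:50 in the FAS, hazard ratio 0.5, 90% and 85% with the event by Day 14, one-sided 0.025, and at least 90% power.

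- Events: D = 100×0.90 + 50×0.85 = 132.5.
- Schoenfeld, 2:1: power = Φ(√(D×2/9)×ln 2 − z).
- √(132.5×2/9) = 5.426; ×0.693 = 3.761; −1.960 = 1.801; Φ = **96.4%**. At the SAP 5.1.1 cut-off 0.0144 (z = 2.186) it is 94.2%. The plan's statement holds.

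**2. Events lost to removal.** The removal rates are assumptions, the same in both arms, with no replacement; a removed subject contributes no event.

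| Removed | D | Power at 0.025 | Power at 0.0144 |
|---|---|---|---|
| 0% | 132.5 | 96.4% | 94.2% |
| 5% | 125.9 | 95.6% | 93.1% |
| 10% | 119.2 | 94.6% | 91.7% |

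This counts lost events only. Keeping resolved subjects in the risk set also pulls the estimate towards no effect, so the table is the favourable end. A simulation under a less favourable assumption (120:60, true rate ratio 2 in favour of RD-X19, removal spread over 48–312 h, 1,500 trials) gave 98.4%, 95.8% and 92.1% at 0%, 5% and 10% removal. The estimated ratio fell from 2.0 to 1.88 and 1.78. Power stays above 90% in both calculations.

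**3. How many removed subjects had already resolved.** Assume exponential times with 85% resolved by 336 h: rate = −ln(0.15)/336 = 0.00565 per hour.

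- By 48 h (about when 6.3 acts): 1 − exp(−0.00565×48) = 23.7%.
- Averaged over 48–168 h in 12-hour steps (discretionary removal): 44.4%, rising from 23.7% to 61.3%.
- With 174 subjects (the SAP 5.1.1 example), 3%, 5% and 10% removal is 5.2, 8.7 and 17.4 subjects. Resolutions set aside: 1.2, 2.1 and 4.1 at 48 h; 2.3, 3.9 and 7.7 over 48–168 h.

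**4. Type I error.** The simulation had no treatment effect, 116:58 subjects (98 mild, split 65:33), a 12-hour diary, censoring at 336 h, removal at 48–168 h unrelated to recovery, and 20,000 trials per scenario (Monte Carlo SE at most 0.002). The test was the one-sided log-rank at 0.025. The Hochberg column is rejection of either primary endpoint.

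| Removed, active / sham | Endpoint 1, SAP rule | Hochberg, either endpoint | Endpoint 1, earlier resolution kept |
|---|---|---|---|
| 0 / 0 | 0.022 | 0.022 | – |
| 10% / 10% | 0.023 | 0.023 | – |
| 0 / 5% | 0.036 | 0.034 | 0.022 |
| 5% / 10% | 0.035 | 0.033 | 0.023 |
| 0 / 10% | 0.057 | 0.052 | 0.024 |
| 10% / 0 | 0.009 | 0.009 | 0.024 |

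Repeat runs of the 0 / 10% case gave 0.052 to 0.066. A 2-point excess in sham gave about 0.026. Balanced removal fixed at 48 h, as under 6.3, gave 0.022 to 0.024 for 3% to 10% removed. The last column shows that the movement comes from setting aside resolutions in combination with unequal removal.

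**The case against.** Much of the case against this point stands.

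- Section 8.5.3 is permissive, sits under device discontinuation and is followed at once by 8.5.4; 7.1.2 stresses completing all visits even after resolution. But 8.5.4 covers only those who stop the device, and the wording of 8.5.3 goes further.
- Several reasons are already handled or would remain exceptions. Subjects lost to follow-up cannot be reached. The adverse-event reason already turns on the subject's interest. For a single subject with an SAE, 8.5.1 stops dosing and continues scheduled visits. Under 9.2, subjects who seek care but are not hospitalised should still attend visits. The discretionary remainder is mainly non-compliance, misuse, and findings that need not prevent a diary entry. Where non-compliance has made the diary unreliable, further entries add little.
- Withdrawing a subject with a newly found disqualifying condition is a defensible safety choice.

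Three stronger readings are tempting, and the documents do not support them.

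- *That SAP 5.2.1 is an error.* It follows openly from an endpoint that requires resolution held to Day 14.
- *That the laboratory withdrawals bias the comparison.* Those under 6.3 rest on samples taken before treatment, so there is no systematic reason for the arms to differ. Because 6.3 replaces these subjects, the power loss in step 2 does not carry over to them.
- *That the trial's type I error is inflated.* This needs a sizeable excess of removals in one arm of a double-blind trial. Neither document suggests one, and Protocol 4.1 reports that no subject discontinued in the preceding 31-subject study. More device-related removals in the active arm, unrelated to recovery, would make the test conservative.

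**Conclusion.** The point holds as an avoidable loss of primary-endpoint data, at low priority. Treated subjects can be, and under 6.3 and 9.1.2 sometimes must be, taken out of the study while staying in the FAS, where they count as censored non-events whatever their diary had shown.

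The planned power remains adequate at up to 10% removal in the calculations above. Balanced removal does not disturb type I error. Only a material difference between arms in discretionary 8.5.3 removal would distort the comparison, and the direction depends on which arm loses more. Every removal rate and timing used here is an assumption; exponential resolution times and removal unrelated to recovery are assumed as well. Removing subjects who have not yet resolved raises a separate question of informative censoring and is not counted here. COVID-19 hospitalisations and subjects lost to follow-up are unaffected.

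**What to change.** - **8.5.3:** state that these reasons end device use only, as in 8.5.4. The symptom diary, and scheduled visits where appropriate, continue to Day 14 unless the subject withdraws consent, cannot be reached, or the investigator judges further procedures against the subject's interest.
- **6.3 and 9.1.2:** stop the device and refer the subject as now, but ask for the diary to Day 14 on the same terms. State whether the 6.3 replacement rule still applies to subjects who stay.
- **SAP 5.2.1:** no change needed; it would still govern subjects who really leave.
- **Optional:** say in 8.5.3 that the default after an SAE is the 8.5.1 course. Add a Final Cohort Sham column to Table 14.1.1, which shows only pooled sham, so that removal can be compared within the primary comparison; Listing 16.2.1 already holds the data by subject.

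The cost is protocol wording, and a few more subjects completing diary entries and visits that are already scheduled.
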